### 1.1 Trial Summary

Subcutaneous insulin therapy in the form of insulin injections or insulin pump therapy has been the cornerstone of insulin delivery for people with Type 1 diabetes (T1D). Despite advancements in monitoring and improved delivery systems, most people with T1D are not able to achieve optimal glucose levels. This raises the need to look for alternative modes of insulin delivery which are non-invasive, likely to be less challenging and more acceptable in long-term. Apart from the mode of administration, oral insulin has the added advantage of replicating a near-physiological state with reduced levels of insulin in blood and thereby confers a 'lower risk of hypoglycaemia'. Many oral insulin preparations have been trialled, especially in the last two decades, although with limited success, especially due to the challenges in absorption of the oral medications. Improved oral drug delivery systems designed to address these barriers have provided a new horizon to explore this avenue further.

A multicentre 12-week clinical trial using oral insulin has recently demonstrated efficacy in adults with early-stage of Type 2 diabetes. Oral insulin caused a clinically meaningful reduction in glucose levels without hypoglycaemia. Hence, there is promise in exploring its potential in T1D. This proposed study is designed as the first step to explore the possibility of using oral insulin in T1D as an adjunct to current management.

The proposed pilot study is a 12-week single-arm observational study in 10 adolescents/adults with T1D in Western Australia. Oral insulin will be administered to participants on closed loop therapy and a range of clinical, metabolic and safety outcomes will be collected. The proposed study aims to provide preliminary data of whether oral insulin is acceptable and can be used as an adjunct therapeutic intervention in individuals with T1D, and to use the information obtained to inform a future randomised controlled trial specifically designed to assess the efficacy of oral insulin as an adjunct to current insulin therapy. The 12-week study will provide sufficient duration to review glycaemic outcomes that can be measured by HbA1c and metrics from continuous glucose monitoring (CGM).

There are no potential ethical issues in the proposed study.

## 2 Rationale / Background

### 2.1 Background summary

Replacement of exogenous insulin is critical in the management of T1D. However, this replacement requires subcutaneous insulin delivery, either as multiple daily insulin injections or by continuous insulin infusion through an insulin pump. Despite advancements in monitoring and improved delivery systems, more than three quarters of people with T1D are not able to achieve optimal glycaemic control (1). Administration of insulin remains a relatively invasive process and is not the most convenient form of

delivery; hence, engagement with insulin administration may be sub-optimal. Oral insulin, however, may be perceived as a more attractive form of insulin delivery, although this has remained an elusive goal. In addition to the ease of administration with an oral preparation, the more significant advantage lies in the different pharmacokinetics having an ability to replicate a near-physiological state, closely mimicking the portal delivery of endogenous insulin. Oral insulin is absorbed by the gastrointestinal tract with its action at the liver, the primary organ of glycaemic control (high portal insulin and low peripheral insulin levels), whereas subcutaneous injections induce high systemic insulin levels, with greater risk of hypoglycaemia and weight gain. Oral insulin, by reducing systemic insulin levels, has the potential to minimise hypoglycaemia, weight gain and may also restore  $\beta$  cell function by reducing the immune response in tissues (2). The multiple perceived benefits of oral insulin delivery have led to various formulations of oral insulin, currently limited to small clinical studies (3).

There are multiple barriers in the oral delivery of unmodified insulin. Degradation of the insulin peptides by the acidic environment of the gut, and poor permeability of the relatively large insulin molecule across the intestinal mucosa are two of the recognised barriers that limit the bioavailability of oral insulin to <1% (4). Developments were therefore aimed at protecting the insulin molecule and facilitating its absorption into the blood stream. An oral insulin preparation (Capsulin) developed by Diabetology Ltd is based on their patented Axcress delivery system (5). It is enteric-coated and has components of well-characterised and “generally regarded as safe” (GRAS) substances. The design of this capsule protects insulin from degradation by proteases in the gut and also enables effective intestinal absorption. The capsule is stable at room temperature for 18 months.

*Preliminary data:* Whitelaw *et al* first demonstrated reduction in glucose levels with oral insulin in eight adults with T1D in a cross-over study which evaluated the plasma insulin and glucose response with a single dose of 150 IU and 300 IU Capsulin (6). Thereafter, a proof of concept study by Luzio *et al* demonstrated a glucose-lowering effect, with only a minimal increase in plasma insulin concentrations with use of Capsulin in 16 individuals with type 2 diabetes (*Figures 1a and 1b*) (7). They also reported a small but significant decrease in HbA1c, weight and triglycerides during the 10-day study period during which participants received 150 IU twice a day of Capsulin.

Figure 1a

[figure not shown]
[figure not shown]
[figure not shown]

Figure 1b

Likewise, a phase 2B trial for type 2 diabetes has just recently been completed (8). This study was a multicentre 12-week trial in 137 participants with a mean HbA1c of 8.1%, randomised to one of the three groups: Group A 75 IU BD, Group B 150IU BD, Group C 300IU BD. *Figure 2* shows HbA1c reduction in the three groups. A reduction in HbA1c >0.5% was met in Group B, while participants with a higher baseline HbA1c (>9%) demonstrated the greatest benefit with a reduction of 1.5%. Furthermore, there were no episodes of hypoglycaemia during the 25,000 dosing events over the 12-week study period. There was also a significant

Figure 2

improvement in the lipid profile with 10% improvement in LDL and total cholesterol and 20% for triglycerides. These promising findings open up avenues to explore the potential of oral insulin in people with T1D.

*Proposed Study:* This pilot study will expand on the findings from these previous studies by exploring the utility of oral insulin in individuals with T1D over a 12-week period.

The proposed study aims to provide preliminary data of whether oral insulin is acceptable and can be used as an adjunct therapeutic intervention in individuals with T1D, and to use the information obtained to inform a future randomised controlled trial specifically designed to assess the efficacy of oral insulin as an adjunct to current insulin therapy. The 12-week study will provide sufficient duration to review glycaemic outcomes that can be measured by HbA1c and metrics from continuous glucose monitoring (CGM) which include time in hypoglycaemia, time in target glucose range and time in hyperglycaemia. We predict a reduction in total subcutaneous insulin dose with supplemental oral insulin will lead to a reduction of systemic hyperinsulinemia. This in turn, has the potential to further reduce hypoglycaemia, which still remains a concern in individuals with T1D (9, 10). This study will also enable us to explore trends of glycaemic variability with daily oral insulin therapy. Improvement in these glycaemic measures are known to reduce the long-term risk of diabetes macro and microvascular complications (11, 12). Liver is the primary site of insulin delivery with oral insulin, unlike subcutaneous insulin, where systemic insulin levels are high in target organs which include liver, muscle and adipose tissue. Hence, the study will also review metabolic parameters with the potential role of oral insulin being cardio-protective.

Our ultimate aim is to improve our understanding of oral insulin and make recommendations for future research to enhance improvements in clinical care to better support people with T1D.

## 2.2 Intervention

*Name and description of the intervention or product(s) used in this trial, including investigational product(s) and comparator product/s (if applicable). Include status of product registration (i.e. registration on Australian Therapeutic Goods Registry, or equivalent).*

1. Oral insulin: Capsulin (Diabetology Ltd) 150 IU once a day, increased to twice a day after a week; to be administered half an hour before food for study duration. This investigational product has been trialled in type 2 diabetes, but not in type 1 diabetes.
2. Hybrid closed loop (HCL) insulin delivery system – Medtronic 670G or Medtronic 770G. This will be the participant's own insulin delivery system
3. Dexcom G6 for participants on Medtronic 670G, as the Medtronic 670G does not have the follow-function to enable monitoring of these participants whilst on the investigational oral insulin.
4. Track caps (Aardex) – The oral insulin capsules will be provided to the participants in bottles fitted with caps which will track how many times the bottles are opened and at what time of day they will be opened. We have used this system effectively in a previous clinical trial (AdDIT-RGS0000002353)

## 3 Trial Aims / Objectives / Hypotheses

The hypothesis of this study is that oral insulin will reduce the patient's dose of subcutaneous insulin. The research question is "Is oral insulin an effective and safe adjunct to conventional therapy in adolescents/adults with T1D?"

The *aims* of this study are to:

1. To perform a pilot study to gather preliminary data required for a randomised controlled trial to assess the effectiveness and safety of oral insulin therapy as an adjunct to standard treatment in individuals with T1D.
2. Determine participant acceptability of adjunct oral insulin therapy and the study procedures.

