		
Capsulin, at the end of the meal challenge. They are provided with lunch half an hour after the oral insulin dosing, and observed for a further 2h prior to discharge.
 
Participants are educated on the appropriate timing of the oral insulin dosing: Capsulin is to be taken half an hour before a main meal.
 
Review home hypoglycaemia management with participant &/or parent. Provide oral insulin for a week
	
insulin 150 IU OD, to ensure stability of the closed loop algorithm. Dose increased to 150 IU BD after one week
 
As per ISPAD & Diabetes Australia guidelines.

VISIT 2 (Week 1)	1.5h	Clinical review of total insulin dose, insulin sensitivity factors, insulin-carbohydrate ratios and CGM metrics.	
		Assessment of Capsulin use, and adverse events	Review of logbook and Aardex history
		Commenced on twice daily 150 IU Capsulin– with appropriate education of use. Provide oral insulin for 5 weeks	
VISIT 3 (Week 6)	45 min	Pump download for pump settings and CGM data. Clinical review of total insulin dose, insulin sensitivity factors, insulin-carbohydrate ratios and CGM metrics.	
		Assessment of Capsulin use, and adverse events	Review of logbook and Aardex history
		Provided with further Capsulin for remaining 6w; twice daily 150 IU dose. Participants are educated on the appropriate timing of the oral insulin dosing: Capsulin is to be taken half an hour before two main meals.	
		Participant to return Dexcom G6 transmitter to researcher	
VISIT 4 (week 12) (STUDY END)	6.5h	Height, weight, BP,	
		
Pump download for pump settings and CGM data
 
Glycaemic measures: HbA1c, total insulin dose, insulin sensitivity factors,
	

		insulin-carbohydrate ratios and CGM metrics	
		Metabolic measures (2mls blood): lipid profile, liver function tests	Fasting bloods
		Meal Challenge (following an overnight fast) with an oral insulin pre-meal bolus. Measure gut hormone responses over 5h - plasma GLP-1 (glucagon like peptide), GIP (glucose dependent insulinotropic polypeptide), plasma glucagon and free insulin. A total of 106 mls will be drawn for 15minutely blood BGL testing and gut hormones during the meal challenge.	
		Participant report of outcomes determined – Appetite and impact on dietary intake, perceived weight loss and well-being.	
VISIT 5 (14w)	30 min	Pump download for pump settings and CGM data	This visit is to ensure that participants are back on baseline therapy.

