## 7 Assessment of Efficacy

### 7.1 Outcomes

1. Total insulin dose (units/kg/day) and the proportion of basal and bolus insulin
2. CGM metrics (13): 12-week CGM data will be collected for variables: Mean SG, % time in range 3.9 to 10 mmol/l, % time in hypoglycaemia (< 3 and < 3.9 mmol/l), % time in hyperglycaemia (>10 and >13.9 mmol/l), and glycaemic variability (coefficient of variation and standard deviation)
3. Auxology: Body mass index Z-scores
4. Metabolic bloods: Lipid profile (Triglycerides, cholesterol, LDL and HDL), Liver function test, HbA1c
5. Gut hormone (glucagon, glucagon-like polypeptide-1 (GLP-1) and glucose-dependent insulinotropic polypeptide (GIP)) responses to a standard meal challenge
6. Safety (Adverse events, Severe adverse events: Severe hypoglycaemia, diabetes ketoacidosis)
7. Recruitment and retention rates
8. Adherence to medication (track caps)
9. Patient-reported outcomes: experiences with oral insulin on appetite, GI disturbances and glycaemic outcomes

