### 7.2 Efficacy assessment

The methods and timing for assessing, recording, and analysing efficacy parameters:

- Insulin profiles and CGM metrics will be assessed at each clinical review – Visit 1,2,3,4. They will also be monitored weekly using the Medtronic and Dexcom databases.
- Other clinical & metabolic outcomes will be measured at study start and study end – Visit 1 & 4
- Adherence to medication and adverse events will be determined at each clinical review – Visit 1,2,3,4
- Patient self-reported outcomes will be determined at the end of the study duration by means of a questionnaire

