### **16.3 Other appendices.**

Participant Self-Reported Outcomes

Logbook for adverse events and concomitant medications

Hypoglycaemia Management Plan

Oral Insulin on Glycaemia Alert Card

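### Aim 2 is acceptability of oral insulin and the study procedures, but no listed outcome measures it directly, and an end-of-study questionnaire would miss those who leave

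*Protocol*

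**What the plan says.** Section 3 gives two numbered aims. The second is to "Determine participant acceptability of adjunct oral insulin therapy and the study procedures", so it has two objects: the therapy and the procedures. Sections 1.1 and 2.1 repeat the first object as a purpose of the study, namely to give "preliminary data of whether oral insulin is acceptable".

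Section 4.1 treats endpoints as not applicable, which leaves Section 7.1 as the only list of outcomes. It has nine items. Those nearest to Aim 2 are:

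- item 7, "Recruitment and retention rates";
- item 8, adherence measured by track caps (Section 6.3 adds capsule counts and self-report);
- item 9, "Patient-reported outcomes: experiences with oral insulin on appetite, GI disturbances and glycaemic outcomes".

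The Visit 4 entry in Section 4.8 describes the participant report differently: "Appetite and impact on dietary intake, perceived weight loss and well-being". Section 7.2 fixes the timing: "Patient self-reported outcomes will be determined at the end of the study duration by means of a questionnaire". Section 16.3 lists an appendix titled "Participant Self-Reported Outcomes", but its items are not in the text at hand.

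Three further provisions decide whose answers count. Section 5.4 lets participants leave without giving a reason, requires no follow-up of them and has them replaced. Section 9.2 sets the sample at 10 with complete data. Section 9.5 admits to the analyses only participants with complete data over the 12 weeks.

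**The concern.** An aim should lead to an outcome that measures it. Here the listed questionnaire topics are perceived effects of treatment: appetite, gut symptoms, glucose, weight and well-being. None asks whether participants would go on taking the capsules, or what they thought of an 8.5-hour first visit, a 6.5-hour last visit, two 5-hour meal challenges and, for 670G users, an added sensor in the opening weeks. The pilot exists to inform a randomised trial, and that trial's designers will need to know which of these procedures to keep.

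The second difficulty is who answers. A person who finds the drug or the procedures unacceptable can leave, and such a person is not followed up, is replaced, and falls outside the analysis set. Even a well-built acceptability item would then be answered mainly by people who tolerated the study.

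This cannot be left to a statistical analysis plan. Such a plan can analyse only what is collected, and the protocol fixes the outcomes, the visit assessments and the timing of the questionnaire.

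**Working it through.** The protocol states no acceptability figure or threshold, so there is no figure of the plan's own to reproduce. The check is a comparison of content, followed by a short formula for the selection effect.

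**Step 1: outcomes against the aim.** Of the nine items in Section 7.1, none is named acceptability. Items 7 and 8 are indirect indicators. Item 9 is the only one in which participants report their own experience.

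**Step 2: the two topic lists.**

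- Section 7.1, item 9 has three topics: appetite, GI disturbances, glycaemic outcomes.
- Section 4.8, Visit 4 has four topics: appetite, dietary intake, perceived weight loss, well-being.
- Shared: one (appetite). Only in 7.1: 3 − 1 = 2. Only at Visit 4: 4 − 1 = 3. Distinct topics: 1 + 2 + 3 = 6.
- Of these six, none is acceptability of the oral insulin and none is acceptability of the procedures.

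**Step 3: what the indirect indicators can show.** Adherence bears on the capsules. Recruitment and retention bear on the study as a whole, including its procedures, because people may decline or leave on account of long visits or meal challenges. They cannot separate one procedure from another, and since Section 5.4 asks for no reason on leaving, retention gives a count without a cause. The protocol does not say how any of them counts toward Aim 2.

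**Step 4: who would be asked.** Suppose 10 participants complete and *w* others leave and are replaced, so 10 + *w* start. Let *p*c be the proportion of completers who find the study acceptable and *p*w the proportion of leavers who do. The result from completers alone is *p*c. The result from everyone who started would be (10*p*c + *w p*w)/(10 + *w*). The difference is

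*p*c − (10*p*c + *w p*w)/(10 + *w*) = [*w*/(10 + *w*)] × (*p*c − *p*w).

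This is zero if nobody leaves and positive whenever leavers are less favourable than completers. The protocol gives no expected number of withdrawals and neither proportion, so the formula fixes the direction under that assumption but not the size. The complete-data rule in Section 9.5 could also drop someone who stayed to the end but lacks another measurement, although that loss need not lean one way.

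**The case against.** The strongest reply is that this is a matter of alignment in the document. Recruitment, retention and adherence are recognised pilot measures that reflect acceptability. Item 9 does ask about experience with the drug, including gut symptoms that could decide whether someone continues. The questionnaire is a separate appendix, and two one-line summaries need not be exhaustive. Much of this stands, and it rules out several stronger readings that a reader might infer.

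- *That Aim 2 cannot be answered.* The listed indirect measures give some evidence, and recruitment and retention reflect in part on the procedures. What is missing is a named, direct measure.
- *That the questionnaire has no acceptability items.* Its items are not shown, so this cannot be known. Only the two descriptions in the protocol body can be judged.
- *That the two topic lists contradict each other.* Neither excludes the other's topics, and one form could cover all six. They differ and should be aligned.
- *That appetite and well-being are invalid without a baseline.* The protocol does not claim to estimate change in them, and experience with a drug can be asked about only after taking it.
- *That the added sensor burdens everyone.* It concerns 670G users only.

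The reply does not meet two points. If the appendix does contain acceptability items, both descriptions omit the very content that serves Aim 2 and need correcting. And whatever the form contains, its timing and the handling of withdrawals leave out early leavers.

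**Conclusion.** The point holds in a limited form. One of the two aims has no direct, named outcome. None of the six questionnaire topics described covers acceptability of the capsules or of the procedures, and only one of the six appears in both descriptions. Indirect evidence exists, so the aim is weakly served and not unanswerable.

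Any direct acceptability result obtained as the protocol stands would lean favourable. That rests on two assumptions: that some participants leave early, and that those who leave are on average less favourable than those who stay. No size can be put on it from the protocol.

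The conclusion also depends on the unseen appendix. If it holds suitable items, the measurement gap becomes a matter of correcting Sections 4.8 and 7.1, while the omission of early leavers remains. The change is worth making because it is cheap and strengthens one of only two aims. The primary outcome, change in subcutaneous insulin dose, is not affected.

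**What to change.** 1. Add to Section 7.1 a named acceptability outcome covering both therapy and procedures. Suitable items are willingness to continue oral insulin, willingness to take part again, and ratings of the burden of dosing, meal challenge and monitoring. If the appendix questionnaire already asks these, amend Section 7.1 and the Visit 4 entry to say so.
2. Use one list of questionnaire topics in Section 7.1 and at Visit 4.
3. State how recruitment, retention and adherence count toward Aim 2.
4. Offer the questionnaire to willing participants who stop early, and report their answers with those of completers. Say in Section 9.5 that the complete-data restriction does not apply to this outcome. Answering would stay voluntary, so the right to leave without giving a reason is untouched.

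The cost is a few questionnaire items and a few minutes per participant, plus short edits to Sections 4.8, 5.4, 7.1, 7.2 and 9.5. The sample size does not change.

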## 4 Trial Design

[figure not shown]
***The scientific integrity of the trial and the credibility of the trial data depend substantially on the trial design and methodology.***

### 4.1 Study Endpoints

Not applicable to this pilot, single-arm observational study.

### 4.2 Study Design

The proposed pilot study is a prospective, 12-week single-arm observational study in 10 adolescents/adults with T1D in Western Australia. The study design is shown in Figure 2, below:

### 4.3 Bias

All participants will receive the same treatment, in this pilot study.

### 4.4 Blinding and Randomisation

All participants will receive the same treatment, in this pilot study.

### 4.5 Device Tracking

Not applicable

### 4.6 Intervention/Product Description

Capsulin™ is, an oral insulin developed by Diabetology Ltd and is based on their patented Access delivery system (5). Capsulin is an enteric-coated capsule which contains unmodified human recombinant insulin with a mixture of well-characterized and “generally regarded as safe” (GRAS) substances which facilitate the transport of insulin through the intestinal wall and into the portal circulation. The capsule is stable at room temperature for 18 months.

Capsulin comes in 150 IU dose capsules, and will be provided to the participants in bottles fitted with a tracking cap (Aardex), which have been effectively used in a previous clinical trial – AddIT (RGS0000002353), to monitor adherence to prescribed dose and time of dosing.

Dose: Capsulin 150 IU BD

This dose is chosen as higher dose (300 IU BD) has no added benefit in a Phase 2A study (8). Oral insulin is absorbed over a period of 1-2 hours and slowly increases to a peak at about 4-5 hours post ingestion. Data suggest that 150 IU dose leads to a reduction of 2 mmol/mol in blood glucose. Capsulin delivers insulin to the liver, where it suppresses hepatic glucose production. As the production of glucose within the liver is related to the concentration of the glucose in the bloodstream, increasing the dose of Capsulin between 150 IU and 300 IU does not lead to a greater fall in glucose. Dose of 150 IU BD resulted in reduction in HbA1c and improvement in metabolic profile with no side-effects.

